Study Protocol and Statistical Analysis Plan

Title: The prevalence and risk factors of coagulopathy in pediatric patients undergoing surgery for epilepsy: a retrospective cohort study

Date: 2022-11-02

Background:

Epilepsy is a common disease of the nervous system with severe consequences. Epidemiological surveys have shown that the prevalence of epilepsy in China is approximately 0.4–0.7%, comprising 7–10 million patients with epilepsy(1), most of whom are children(2). Although most symptoms of epilepsy can be controlled with the use of anti-seizure medications (ASMs), there are still a few patients who cannot achieve satisfactory seizure control with such medications or cannot tolerate their side effects, thus requiring surgical treatment. Surgical treatment of epilepsy has been recognized as a valuable treatment option for carefully selected patients to achieve better seizure control and quality of life(3). Compared to adults, children with epilepsy with indications for surgery usually have a better prognosis after surgical treatment(4–8). Many children undergoing surgery for epilepsy have a long history of using ASMs. Moreover, ASM therapy usually consists of multiple varieties of drugs, thereby bringing significant attention to the side effects of ASMs, especially those that may be relevant in the perioperative surgical setting.

ASMs have been associated with multiple adverse effects on platelets and the coagulation system(9). Valproic acid (VPA), one of the most commonly used traditional ASM, has been reported to cause multiple hematologic abnormalities, including thrombocytopenia, platelet aggregation dysfunction, fibrinogen (FBG) depletion, bone marrow suppression, decreased factor XIII, and acquired von Willebrand disease(10–17). However, the wide use of novel ASMs in recent decades has led to decreased reports of adverse events. The hematologic consequences of these novel ASMs or combined therapies are rarely reported. Few studies have suggested that levetiracetam (LEV) does not cause clinically significant or relevant hematological disorders(18).

Such reported side effects may be more significant in pediatric patients with epilepsy due to individual differences in age, weight, and pharmacokinetic action of the body on the drugs. The incidence of coagulopathies has been reported to be higher in children than in adults, especially hypofibrinogenemia(19,20). Nevertheless, whether these coagulation dysfunctions increase the risk of perioperative bleeding remains controversial. Most investigators suggest that ASMs, including VPA, are not associated with surgery-related blood loss or transfusion requirements(21–23). However, a few studies have suggested that considering the extra risk of perioperative bleeding, VPA should be discontinued before surgery(14).

Objectives:

This retrospective analysis of 390 children with epilepsy systematically investigated the incidence and risk factors of preoperative coagulation dysfunction in children undergoing surgery for epilepsy and their impact on surgery, with the objective to provide detailed and valuable clinical information.

Design:

This study was a retrospective cohort study.

Methods:**Study population**

This retrospective study focused on children who underwent surgery for epilepsy between

January 2015 and December 2021 at the Neurosurgery Department of our hospital. Consecutive patients under 18 years who satisfied the following criteria were enrolled: a discharge diagnosis of "epilepsy" according to the International Classification of Diseases (ICD-10) and surgical treatment during the hospitalization. The following clinical data were collected: sex, age, weight, epilepsy course, and anti-seizure therapy. The initial laboratory data after admission included platelet count (PLT), prothrombin time (PT), activated partial thromboplastin time (APTT), FBG, alanine aminotransferase (ALT), and aspartate aminotransferase (AST). The patients' record of intra/post-operative transfusion or no transfusion was obtained from the medical records. The researchers also collected data on non-epileptic children who underwent non-epilepsy neurological surgery and were admitted at the same period from the Hospital Information System (HIS) as a control cohort. A total of 539 patients were initially included in the study. Patients were excluded if the clinical information or laboratory examinations were incomplete, or had concomitant diseases affecting coagulation or liver function. Patients were also excluded if they refuse to be enrolled to the study. Overall, 390 epilepsy cases and 104 non-epilepsy controls were included in the study (figure 1). All the surgeries were performed by the same surgeon.

ASM therapy

All ASM therapies were administered by a specialist at our hospital and recorded once the patient was admitted. Therapy was defined as the ASMs taken at the time of admission, and all ASM therapies were continued till surgery at our center. Based on the frequency of use of ASMs, drugs taken over 10 times in all cases were included in the statistics, including, VPA, LEV, oxcarbazepine (OXC), carbamazepine (CBZ), topiramate (TPM), and lamotrigine (LTG). Simultaneous administration of two or more types of ASMs was defined as "polytherapy."

Laboratory tests

Following the clinical routine at our center, routine blood tests, coagulation function tests, and liver function tests were performed after admission. The following laboratory data were collected: PLT, PT, APTT, FBG, ALT, and AST levels. Abnormal coagulation function/coagulation dysfunction/coagulopathy was confirmed if the values obtained were more (or less) than the highest (or lowest) normal range values of either PT, APTT, FBG, or PLT (PT>14.5 s, APTT>45 s, FBG< 2 g/L, PLT<150×10⁹/L). Abnormal liver function was defined as values higher than the highest range of ALT or AST (ALT>42 U/L, AST>59 U/L).

Statistical analyses

Categorical variables are presented as absolute (n) and relative frequencies (%). Continuous variables are shown as the mean (\pm standard deviation) or median (interquartile range), where applicable. The χ^2 test was used to evaluate differences among categorical variables. Continuous variables with normal and skewed distributions were compared using the t-test and Wilcoxon rank-sum test, respectively.

Univariate logistic regression analyses were performed to identify possible determinants of coagulation function. Possible relevant variables were included as covariates for multivariate logistic regression analysis to further filter out distractions. The results of the univariate and multivariate logistic regression analyses are presented as OR and 95% CI. The researchers used

R V4.1.2 to conduct statistical analyses.

Reference

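### Operation type is not collected, so the coagulopathy–transfusion comparison cannot be checked or adjusted for differences in procedure mix

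*Combined protocol and SAP*

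**What the plan says.** The Objectives section of the combined protocol and SAP sets out to study "risk factors of preoperative coagulation dysfunction in children undergoing surgery for epilepsy and their impact on surgery". The Study population section opens by limiting the study: "This retrospective study focused on children who underwent surgery for epilepsy between" "January 2015 and December 2021 at the Neurosurgery Department of our hospital". The criteria then listed are age under 18 and "a discharge diagnosis of 'epilepsy' according to the International Classification of Diseases (ICD-10) and surgical treatment during the hospitalization".

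On data, the same section says: "The following clinical data were collected: sex, age, weight, epilepsy course, and anti-seizure therapy". It adds six laboratory values (PLT, PT, APTT, FBG, ALT, AST). The surgical outcome is described in one sentence: "The patients' record of intra/post-operative transfusion or no transfusion was obtained from the medical records". Type, extent and duration of the operation and blood loss are not listed there or under Laboratory tests.

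The Statistical analyses section describes a χ² test for categorical variables and logistic regression for determinants of coagulation function, with covariates that are not named. It describes no model for transfusion. The one statement bearing on comparability of the operations is "All the surgeries were performed by the same surgeon".

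**The concern.** The need for transfusion plausibly depends on which operation was done. The documents give no figures on this, so it is an inference, but a natural one. If children with coagulopathy tend to have different operations from children without it, a crude comparison mixes the effect of coagulopathy with the effect of the operation. That could happen, for example, because age or drug regimen influences both.

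The Background calls the link between coagulation dysfunction and perioperative bleeding controversial and cites work on both sides. A confounded comparison could add a false alarm or a false reassurance to that dispute. Without the procedure field the investigators cannot restrict, stratify or adjust by operation, and cannot even tabulate procedure mix by coagulopathy status to show that the problem is absent.

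**Working it through.** The plan states no effect size, power or transfusion rate, so there is no figure of its own to reproduce. The check has two parts.

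**Part 1: what the text provides**

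| Needed for the impact-on-surgery aim | In the plan? |
|---|---|
| Exposure: coagulopathy | Yes, defined from PT, APTT, FBG and PLT |
| Outcome | Yes, transfusion yes/no |
| Operation type or extent | In no list of collected data |
| Model or strata for transfusion | None described; the general χ² test is what applies |
| Criterion that the operation was for epilepsy | In the framing sentence, not in the listed criteria |

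**Part 2: how much procedure mix could matter**

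Only the 390 comes from the documents. All other inputs are assumptions for illustration.

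- Higher-bleeding operations: 0.70 × 390 = 273 children, transfusion risk 0.40.
- Lower-bleeding operations: 0.30 × 390 = 117 children, transfusion risk 0.02.
- No true effect: within each group, transfusion is independent of coagulopathy.
- Coagulopathy prevalence is a in the higher-bleeding group and b in the lower-bleeding group.

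Pooled transfusion risk with coagulopathy = (273a × 0.40 + 117b × 0.02) / (273a + 117b). Without coagulopathy, replace a and b by 1 − a and 1 − b.

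Worked case, a = 0.35 and b = 0.15:

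- With coagulopathy: (95.55 × 0.40 + 17.55 × 0.02) / 113.1 = 38.571 / 113.1 = 34.1%.
- Without: (177.45 × 0.40 + 99.45 × 0.02) / 276.9 = 72.969 / 276.9 = 26.4%.
- Odds ratio = (0.3410 / 0.6590) / (0.2635 / 0.7365) = 1.45.

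| a | b | Risk with coagulopathy | Risk without | Pooled OR (true OR 1.00) |
|---|---|---|---|---|
| 25% | 15% | 32.2% | 27.6% | 1.25 |
| 35% | 15% | 34.1% | 26.4% | 1.45 |
| 15% | 35% | 21.0% | 30.6% | 0.60 |
| equal | equal | 28.6% | 28.6% | 1.00 |

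The last row is 0.70 × 0.40 + 0.30 × 0.02 = 0.286 in both groups.

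**Sensitivity to the assumed risks**

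A second set of assumptions uses transfusion risks of 5% vs 20%, 5% vs 40% and 10% vs 50% in lower- and higher-bleeding operations. The share of higher-bleeding operations is set directly in each coagulopathy group.

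| True OR within operation type | Higher-bleeding share, with vs without coagulopathy | Pooled OR for the three risk pairs |
|---|---|---|
| 1.0 | 50% vs 50% | 1.00, 1.00, 1.00 |
| 1.0 | 60% vs 40% | 1.32, 1.50, 1.47 |
| 2.0 | 50% vs 50% | 1.91, 1.72, 1.72 |
| 2.0 | 40% vs 60% | 1.45, 1.14, 1.17 |

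For example, row two with 5% vs 40%: 0.6 × 0.40 + 0.4 × 0.05 = 0.26 against 0.4 × 0.40 + 0.6 × 0.05 = 0.19, so OR = (0.26 / 0.74) / (0.19 / 0.81) = 1.50.

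The shrinkage in row three occurs without any imbalance. It reflects non-collapsibility of the odds ratio and is not confounding. Confounding arises only where the mix differs.

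**The case against.** There is a good deal to say on the other side.

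- **The cohort is restricted.** A reader might infer from the listed criteria that any operation in a child coded with epilepsy was eligible, a shunt revision for instance. The documents do not support that. The title, the objective and the opening sentence of Study population all limit the study to surgery for epilepsy, in one neurosurgery department, and the controls are defined by surgery unrelated to epilepsy. What stands is narrower: the listed criteria do not carry that restriction, and the restriction itself names no operations.
- **Collected variables may do part of the work.** If operation type is linked to coagulopathy only through age, weight or drug therapy, correct adjustment for those variables would remove that confounding without the procedure field. It would be too strong to say that such adjustment cannot help. But no transfusion model is described, and the condition cannot be checked without the field.
- **One surgeon did every operation.** That holds the operator constant, not the operation.
- **The size is assumed.** This is correct. The documents give no procedure mix and no transfusion rate by operation, and with a balanced mix a null effect stays null.
- **Pooling is legitimate in itself.** A reader might infer that including low-bleeding operations biases the result by dilution. It does not. If a 15-point risk difference were confined to 70% of operations and coagulopathy were equally common in both groups, the pooled 0.70 × 15 = 10.5 points would be the valid average for the declared population.

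**Conclusion.** The point holds for the impact-on-surgery aim only. As written, the transfusion comparison is crude and pooled over operations that are not recorded, and the plan offers no means of detecting or correcting a difference in procedure mix.

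Under the first set of assumptions, procedure mix alone moves a null odds ratio to anywhere from about 0.60 to 1.45. Those values depend on the assumed 70/30 split, the 40% and 2% risks and the 15–35% coagulopathy prevalences, none of which is documented. Serious distortion requires the mix to differ by coagulopathy status, and the documents give no evidence on that in either direction.

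A reader might also infer that a real effect would be reversed. The calculations do not show this: the values below 1 assume no true effect, and a true odds ratio of 2.0 under the adverse 40% vs 60% imbalance falls to 1.14–1.45, still above 1.

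The prevalence and risk-factor results for preoperative coagulopathy are not affected, because the laboratory values are the first taken after admission. The change is worth making because it is cheap and removes a doubt that the present data cannot settle.

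**What to change.** 1. State in the listed criteria that the index operation was performed to treat epilepsy, as confirmed in the operation record.
2. Abstract procedure type from the existing operation records of the 390 children, in a few categories fixed beforehand: resection or disconnection, intracranial electrode implantation, stimulator implantation, other.
3. Tabulate procedure type by coagulopathy status.
4. Stratify or adjust the coagulopathy–transfusion analysis by procedure type, together with age, weight and anti-seizure therapy, which are already collected. Keep all 390 children.
5. Report the resection/disconnection subset as a secondary analysis. Making it the main analysis would be a matter of preference; the defect does not require it.

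The cost is one extra field per child and some loss of precision from the added covariate. Categories should stay few, because those with little bleeding may hold very few events: under the assumed inputs, 117 × 0.02 ≈ 2 transfusions against 273 × 0.40 ≈ 109. No treatment or visit changes.

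### The plan aims to assess the impact of coagulopathy on surgery, but as written only an unadjusted chi-square test reaches transfusion, the one surgical outcome listed

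*Combined protocol and SAP*

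**What the plan says.** The Objectives state that the study "systematically investigated the incidence and risk factors of preoperative coagulation dysfunction in children undergoing surgery for epilepsy and their impact on surgery". The title is narrower: "The prevalence and risk factors of coagulopathy in pediatric patients undergoing surgery for epilepsy". The Background explains the interest in surgical impact: "whether these coagulation dysfunctions increase the risk of perioperative bleeding remains controversial".

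Under Study population, the only surgical outcome is transfusion: the "record of intra/post-operative transfusion or no transfusion was obtained from the medical records". Blood loss, transfused volume, operating time and complications are not listed. The same section says: "The following clinical data were collected: sex, age, weight, epilepsy course, and anti-seizure therapy". Type or extent of surgery is not listed.

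Statistical analyses gives a general chi-square rule for categorical variables, then two sentences on regression: "Univariate logistic regression analyses were performed to identify possible determinants of coagulation function", followed by "Possible relevant variables were included as covariates for multivariate logistic regression analysis to further filter out distractions". Odds ratios with 95% confidence intervals are promised for these regressions. Transfusion is not mentioned anywhere in that section.

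**The concern.** One stated objective has no analysis of its own. The default that covers it is a crude test, which yields a p-value but neither an effect size nor an interval.

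Coagulopathy is not randomised here. If a factor relates to both coagulopathy and transfusion, a crude comparison can create an association or hide one.

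- **Age and weight.** The Background ties them to the drugs' side effects, in hedged terms: "Such reported side effects may be more significant in pediatric patients with epilepsy due to individual differences in age, weight". It gives no direction among children. Their link to transfusion is my assumption; no section states it.
- **Valproate.** The Background reports that it lowers platelets and fibrinogen, which are part of the coagulopathy definition under Laboratory tests. It also reports platelet aggregation dysfunction and reduced factor XIII, which are not. Valproate could therefore act on bleeding by a path outside the exposure. Against that, the Background says most investigators find no link between these drugs and blood loss or transfusion.

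At stake is a misleading contribution to a question that the protocol itself calls unsettled.

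**Working it through.** The plan states no rates, power or effect size, so there is no figure to reproduce.

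**Step 1. Which rule reaches transfusion?** Taking Statistical analyses rule by rule:

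- Counts and percentages: description only.
- Chi-square: covers any categorical comparison, so transfusion by coagulopathy status. No covariates, no effect estimate.
- t-test and Wilcoxon: continuous variables, not applicable.
- Univariate logistic regression: the dependent variable is coagulation function.
- Multivariate logistic regression: continues the univariate step; names no other dependent variable and no covariates.
- OR and 95% CI: promised for the logistic models only.

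Only the chi-square rule remains.

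**Step 2. What could a crude test do?** N = 390 is from Study population. Everything else is assumed: a share y = 0.40 of children are young; coagulopathy risks are cY (young) and cO (older); transfusion risks are tY and tO; there is no effect of coagulopathy within either age group.

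- P(C) = y·cY + (1−y)·cO
- p1 (transfused, with coagulopathy) = [y·cY·tY + (1−y)·cO·tO] / P(C)
- p0 (transfused, without) = [y·(1−cY)·tY + (1−y)·(1−cO)·tO] / [1−P(C)]
- crude OR = [p1/(1−p1)] / [p0/(1−p0)]

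Worked case, strong confounding and low transfusion rate (c 50% v 25%, t 20% v 7%):

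- P(C) = 0.20 + 0.15 = 0.35
- p1 = (0.040 + 0.0105)/0.35 = 0.144
- p0 = (0.040 + 0.0315)/0.65 = 0.110
- crude OR = 0.1686/0.1236 = 1.36
- overall transfused = 0.0505 + 0.0715 = 12.2%
- z = (p1−p0)/√[0.122·0.878·(1/136.5 + 1/253.5)] = 0.0343/0.0347 = 0.99
- rejection ≈ Φ(0.99−1.96) + Φ(−0.99−1.96) ≈ 0.17; simulating 200,000 studies gives 0.174

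All null cases (simulated rejection at nominal 5%; the plan does not say whether a continuity correction is used):

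| Coagulopathy, young v older | Transfusion, young v older | Overall transfused | Crude OR | Rejection | With correction |
|---|---|---|---|---|---|
| 40 v 30% | 15 v 8% | 10.8% | 1.08 | 6% | 4% |
| 45 v 25% | 15 v 7% | 10.2% | 1.20 | 9% | 6% |
| 50 v 25% | 20 v 7% | 12.2% | 1.36 | 17% | 14% |
| 40 v 30% | 50 v 30% | 38% | 1.09 | 7% | 6% |
| 45 v 25% | 50 v 25% | 35% | 1.27 | 19% | 16% |
| 50 v 25% | 60 v 25% | 39% | 1.47 | 43% | 39% |

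If age is unrelated to coagulopathy (30% at all ages) or to transfusion (30% at all ages), the crude OR is 1.00 and rejection without correction is 5%. More extreme assumptions go further: with half the children young, coagulopathy 60 v 30% and transfusion 60 v 20%, the crude OR is 1.66 and rejection about 68%.

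**Step 3. The opposite direction.** Let the true OR be 1.5 within each age group, with coagulopathy less common in the young (25 v 50%). With transfusion of 20 v 7% in those without coagulopathy, the risks with it are 0.375/1.375 = 0.273 and 0.1129/1.1129 = 0.101. Then p1 = (0.10·0.273 + 0.30·0.101)/0.40 = 0.144, p0 = (0.30·0.20 + 0.30·0.07)/0.60 = 0.135, and the crude OR is 1.08. Power is 6% crude and about 25% with an age-stratified (Mantel-Haenszel) test. At transfusion of 60 v 25% the crude OR is 0.99, with power 5% against 41%.

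**Step 4. Precision and events.** Without any confounding, 390 children give 80% power (two-sided 5%) only for an OR of about 1.8 (coagulopathy 40%, transfusion 40% in those without it) to 3.3 (20% and 5%). A non-significant p-value without an interval would therefore say little. At the usual 10 events per model term, three terms need about 30 transfused (30/390 = 7.7%) and four need about 40 (40/390 = 10.3%).

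**The case against.** **The plan is silent; it does not choose a crude analysis.** The chi-square sentence is a general default, and the multivariate sentence does not expressly exclude a transfusion model. This stands in part. A reader might infer that the plan commits to an unadjusted transfusion comparison; it does not say so. But if an adjusted model was intended, its outcome, exposure and covariates are unstated, so the same text is needed.

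**The bias is assumed.** This stands. No section links age or weight to transfusion, and the illustrated false-positive rate starts at 5%. With about 10% to 12% transfused, mild and middling confounding give 6% and 9%, or 4% and 6% with a continuity correction. A reader might infer that the transfusion result is wrong, or biased upwards; the documents support neither.

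**Adjustment would not settle the question.** This also stands. Procedure type is not listed, so residual confounding remains. Product and indication for transfusion are not listed either: if products were given because a test was abnormal, the association is partly circular and no covariate removes that. A reader might take an adjusted OR as causal; these data would not support that.

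**Conclusion.** The gap holds on the text: impact on surgery is an objective, transfusion is its only listed outcome, and as written only an unadjusted test without an effect estimate reaches it. That should be fixed, because the exposure is not randomised and the main candidate covariates are already collected.

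The consequence is uncertain. Under the tabulated assumptions it runs from no bias to a crude OR of 1.47 and 43% false positives when nothing is there; with confounding the other way, a true OR of 1.5 can be almost hidden. These figures rest on invented rates and a single two-level confounder. They show what is possible and do not predict this study's result.

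A reader might extend the point to the whole study. That would be wrong: the title covers prevalence and risk factors, and those analyses do not depend on how transfusion is compared.

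**What to change.** Add to Statistical analyses:

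- **Model.** In the 390 epilepsy children, excluding the 104 controls, a logistic regression with transfusion (yes/no) as dependent variable and any coagulopathy as exposure, adjusted for age and weight, and for valproate use if the number transfused allows.
- **Size of model.** About 30 transfused children for three terms and about 40 for four. With fewer, use fewer terms or a penalised fit.
- **Reporting.** The number transfused, and the adjusted OR with 95% CI beside the crude OR. Interpret only the coagulopathy OR, since age and weight will be correlated.
- **Status.** The plan is dated November 2022 and already reports final cohort counts. Label the model post hoc if it is added after the data were examined.
- **Limitations.** Procedure type is not listed as collected, and transfusion prompted by an abnormal test would make the association partly circular.

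The cost is one model on data already held, plus two sentences of limitation. The interval may widen slightly: in simulations with an assumed age–weight correlation of 0.90, the standard error of the log OR rose by 0.4% with no age effect and by 5% to 10% under strong confounding. Those runs rest on further assumed coefficients and had no valproate term, so they are only a rough guide. The result may also be less clear-cut.

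### Do the polytherapy and drug odds ratios need a term for the rarer anti-seizure medications left out of the analysis?

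*Combined protocol and SAP*

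**What the plan says.** The ASM therapy section of the combined protocol and SAP makes three statements in sequence.

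- Exposure: "Therapy was defined as the ASMs taken at the time of admission".
- Drugs analysed: "drugs taken over 10 times in all cases were included in the statistics". Six are named: valproic acid (VPA), levetiracetam, oxcarbazepine, carbamazepine, topiramate and lamotrigine.
- Polytherapy: "Simultaneous administration of two or more types of ASMs was defined as" polytherapy.

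The exclusions under Study population ("Patients were excluded if the clinical information or laboratory examinations were incomplete, or had concomitant diseases affecting coagulation or liver function", plus refusal) do not remove children on rarer ASMs from the 390 cases. The Statistical analyses section describes the adjusted model only in general terms: "Possible relevant variables were included as covariates for multivariate logistic regression analysis to further filter out distractions". It does not list the covariates, and it does not say whether polytherapy enters a regression, alone or beside the drug indicators. Results are given as OR and 95% CI.

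**The concern.** Suppose polytherapy counts every ASM while only six drugs have indicators. A child on one listed and one rarer drug is then coded as polytherapy with a single listed drug. In a model holding both kinds of term, the omitted rarer drug is positively related to polytherapy and, given polytherapy, negatively related to the listed drugs. If rarer drugs raise the risk of coagulation dysfunction, the polytherapy OR is pushed up and the listed-drug ORs down. If they are protective, the reverse happens.

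Risk factors are a stated objective, and the Background says of newer and combined treatment: "The hematologic consequences of these novel ASMs or combined therapies are rarely reported". A spurious polytherapy effect would therefore fall where readers have little other evidence to check it against.

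**Working it through.** The plan gives no figure to reproduce on this point. It supplies 390 cases, six analysed drugs and the frequency rule. A drug left out has at most 10 uses, so at most 10/390 = 2.6% of cases if each use is one child. Everything else below is assumed.

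**1. Size of the bias in the joint model.** Drug combinations were enumerated exactly, and a large-sample logistic model was fitted to the six indicators plus all-ASM polytherapy, omitting rarer drugs. Assumed: independent use at 45/35/35/12/20/18% for VPA, levetiracetam, oxcarbazepine, carbamazepine, topiramate and lamotrigine, before requiring at least one ASM; baseline risk 25%; true VPA OR 2.00; true polytherapy OR 1.00; each rarer drug used at 10/390. Shift in standard errors (SE) = |ln(fitted OR / true OR)| / SE at n = 390.

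| Rarer drugs (share of cases) | Rarer-drug OR | Polytherapy OR (SE) | Shift | VPA OR (SE) | Shift |
|---|---|---|---|---|---|
| 1 (2.9%) | 2 | 1.088 (0.37) | 0.084/0.37 = 0.23 | 1.906 (0.28) | 0.048/0.28 = 0.17 |
| 1 (2.9%) | 4 | 1.188 (0.36) | 0.172/0.36 = 0.48 | 1.803 (0.28) | 0.104/0.28 = 0.37 |
| 3 (8.6%) | 2 | 1.229 (0.35) | 0.206/0.35 = 0.59 | 1.783 (0.27) | 0.115/0.27 = 0.43 |
| 3 (8.6%) | 4 | 1.517 (0.34) | 0.417/0.34 = 1.23 | 1.566 (0.26) | 0.245/0.26 = 0.94 |
| 6 (16.3%) | 2 | 1.376 (0.33) | 0.319/0.33 = 0.97 | 1.688 (0.25) | 0.170/0.25 = 0.68 |
| 6 (16.3%) | 4 | 1.889 (0.32) | 0.636/0.32 = 1.99 | 1.398 (0.25) | 0.358/0.25 = 1.43 |

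At a rarer-drug OR of 1 there is no bias. In this large-sample calculation, a pooled indicator for any other ASM returns 2.00 and 1.00 in every row.

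**2. What the pooled term costs.** A simulation at n = 390 (2,000 datasets per setting, listed drugs and polytherapy truly null, 30% base risk, six rarer drugs with about 14, 27 or 38 users in total) gives this root-mean-square error for the polytherapy log-OR in the joint model:

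| Rarer-drug OR | Without term (14 / 27 / 38 users) | With term |
|---|---|---|
| 1 | 0.43 / 0.41 / 0.39 | 0.47 / 0.46 / 0.45 |
| 1.5 | 0.45 / 0.44 / 0.45 | 0.47 / 0.45 / 0.46 |
| 1.75 | 0.45 / 0.48 / 0.51 | 0.46 / 0.46 / 0.44 |
| 2 | 0.47 / 0.52 / 0.56 | 0.47 / 0.47 / 0.46 |
| 3 | 0.53 / 0.64 / 0.76 | 0.47 / 0.46 / 0.46 |

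The term loses at OR 1 and brings no gain at 1.5. Break-even lies between 1.5 and 1.75 with 27 to 38 users, and near 2 with 14. Standard errors grow by about 7 to 19% for polytherapy and 5 to 12% for VPA. With about 14 users, separation occurs in about 1% of datasets at OR 1 and 11% at OR 0.5.

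**3. Other models the plan allows.** Over rarer-drug ORs of 1.5 to 3 (true value 1), six indicators without polytherapy give VPA 0.92 to 0.99. Univariate models give VPA 0.95 to 0.99 and polytherapy 1.01 to 1.13. The bias matters mainly in the joint model.

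**4. Other remedies.** Counting only listed drugs towards polytherapy removes most of the polytherapy bias but not necessarily the VPA bias. With one to three ASMs per child, about 27 users and rarer-drug ORs of 1.5, 2 and 3, the share of VPA log-OR bias left is ln 0.92/ln 0.86 = 0.55, ln 0.88/ln 0.78 = 0.51 and ln 0.82/ln 0.67 = 0.50. Fitting polytherapy without the drug indicators is no safe fallback: with a true VPA OR of 2 or 3, null polytherapy and harmless rarer drugs, it gives polytherapy 1.27 or 1.46. The joint-model bias at a rarer-drug OR of 1.5 with 27 users is 1.20.

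**The case for a change.** The strongest case for acting is that no sentence settles which drugs count, that separate calculations with different inputs agree on the direction of the bias, and that it can be large. With 38 users and an OR of 3 shared by all six rarer drugs, polytherapy reads 1.94 with 43% false positives. Therapy was recorded at admission, so recoding needs no new data. The count of rarer-ASM users and the covariate list would help any reader interpret a polytherapy OR, whatever the bias.

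The mechanism stands, and so does the value of those details in the report. The case for altering the analysis does not. The harm needs four things together: all ASMs counted, both kinds of term in one model, rarer drugs that affect coagulation, and enough users. Only the first has support in the text. The high figures come from the far end of the assumed range. With a single rarer drug (about 9 users) under the simulation's drug mix, polytherapy is 1.07 at OR 1.5 and 1.14 at OR 2. The Background's remark that evidence is scarce gives no ground for assuming a large effect, just as it gives none for assuming zero.

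**Conclusion.** No change to the plan follows. The frequency rule selects which drugs are analysed individually; it does not redefine ASM. Taken with the admission-based definition of therapy, the natural reading is that polytherapy counts every ASM. What is left unsaid (that reading, the number of children on unlisted drugs, the covariates) is detail that analysts can supply when they report, from data already held.

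The one concrete change of method, a pooled term in the main model, is a trade-off with no demonstrated gain: it helps only if rarer drugs carry an OR above roughly 1.5 to 2, depending on the number of users. If analysts do fit polytherapy and the six indicators together, a sensitivity analysis with that term, or without those children, is enough. The conclusion rests on assumed drug frequencies, base risks of 25 to 30% and assumed rarer-drug effects. The true size is unknown. It is well below one standard error if only one rarer drug was in use, and could exceed one standard error if several were and each strongly affected coagulation.
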